6. INVESTIGATIONAL MEDICINAL PRODUCT

Not applicable.

6.1 Name and description of investigational medicinal product(s)

6.2 Summary of findings from non-clinical studies

6.3 Summary of findings from clinical studies

6.4 Summary of known and potential risks and benefits

6.5 Description and justification of route of administration and dosage

6.6 Dosages, dosage modifications and method of administration

6.7 Preparation and labeling of Investigational Medicinal Product

6.8 Drug accountability

7. METHODS

7.1 *Study parameters*

Based on literature about the outcome following a DRF (19-24), and experts' opinions, we decided to use 5 outcome measures. The main outcome measure is function. Other outcome measures used are the range of motion, grip strength, dexterity, and pain.

7.1.1 *Main study parameter/endpoint*

Research has shown that DRF-patients suffer more on long term from function restrictions than pain (15,16). Therefore, function is the main outcome measure. Function is measured using the Patient Rated Wrist/Hand Evaluation (PRWHE). This instrument is developed to measure disability during usual and specific activities, and it also documents pain and aesthetics. The PRWHE is derived from the PRWE and contains some extra questions about aesthetics. Because the PRWHE retains the originally validated questions, format and scoring system of the PRWE, it can be treated as the PRWE (59). A study that critically reviewed the available outcome assessment tools, showed that the PRWE is the most responsive instrument to measure outcome in DRF-patients (60). The PRWE is a self-rated questionnaire, and its mean completion time is 4 minutes (61). It consists of 15 questions, divided in 3 domains; pain, functional activities, and usual activities. The patients have to rate the severity of their pain or disability in different situations. The final score of the PRWE and PRWHE lies between 0-100, where 0 represents the best and 100 represents the worst outcome. The PRWE is found to be reliable and valid, and therefore provides a simple and quick method to measure patient-rated pain and disability (61).

7.1.2 *Secondary study parameters/endpoints*

Secondary outcome measures are dexterity, active range of motion, grip strength, and pain. The Sequential Occupational Dexterity Assessment (SODA) is used to determine dexterity. The SODA is a valid and reliable instrument that measures bimanual dexterity during activities of daily living (68). The SODA consists of 12 tasks, and it takes 20 minutes to complete it. The performance on the tasks is scored by the experimenter. The score for each task is build up by two different components. One component concerns how the task is performed, and the other component concerns the difficulty the patient experiences during the execution of the task. For some tasks, only one hand is scored, while for other tasks both hands are scored. The final score

ranges from 0-108, where 0 means that the patient is unable to perform any of the tasks, and 108 means that all tasks were performed as requested without any difficulty (68).

Range of motion (ROM) is determined using a digital goniometer. Because unrestricted movement is essential for normal function, wrist movement in all directions is measured; flexion, extension, radial deviation, ulnar deviation, pronation and supination. The literature available concerning the amount of measurements needed to provide reliable outcomes, is contradicting (69). Some researchers have found that only one measurement is sufficient (70), whilst others have found that the average of several measurements is more reliable than one measurement (71). It is recommended to use the average of multiple measurements in the ROM that shows large variation or a systematic increase (69). We repeatedly measured the different ranges of motion, and this provided consistent results. Based on this we decided to use a single measurement of each aspect of ROM (i.e. flexion, extension, abduction, adduction, supination, and pronation). To control for within-group variability, ROM is measured on both hands.

Grip strength is important for the execution of many occupational activities (72). It is measured using a hydraulic dynamometer, which is found to be reliable and valid (73). Research has shown that the position of the wrist can influence the maximal grip strength that can be applied. This is especially the case when the wrist is in ulnar or radial deviation, which is one of the deformities that is common after a DRF malunion (74). Therefore, it is useful to determine different grip strengths; grasp, tip pinch, key pinch, and three-jaw chuck pinch (72,73). The measurements will be conducted using a standardized protocol (73), to counter the effects of confounders. The mean of three trials has the highest test-retest reliability (73), and therefore, it is decided to measure the strength of each grip three times. To control for within-group variability, grip strength is measured on both hands.

Two dimensions of pain are measured using a Visual Analog Scale (VAS) (75); pain intensity and pain relief (76). This results in a score between 0 and 100, where 0 represents severe pain and low pain relief, and 100 represents no pain and large pain relief.

7.1.3 *Other study parameters*

Confounding factors that might influence the dependent variables are age, motor imagery ability, type of fracture, occupation, sport activities and involvement of their casted hand in activities. The patients will be asked for their occupation, sport activities and involvement of the

casted hand in activities. The confounding factors will be included in the statistical analysis as covariates to control for their influence.

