Three weeks later, which is 4 weeks after injury, the patients return to the hospital to remove the cast. At that moment, the first measurements will be performed. All tests will be performed by the study coordinator. Directly after cast removal, when they are still at the hospital, dexterity, the level of pain and pain relief, grip strength and range of motion will be determined. The PRWHE will be performed one day later by phone. Two weeks after cast removal, the second measurements will be conducted. Function, dexterity, the level of pain and pain relief, grip strength and range of motion will be measured.

The measurements will take place in the University Medical Center Groningen. The PRWHE and the VAS can be scored by the patients themselves, while the measurements with the SODA, goniometer and dynamometer will be conducted by the study coordinator. It is expected that the first measurements will take 30 minutes to complete, and the second measurements 35 minutes.

As explained in chapter 7.1, function is measured using the PRWHE. The PRWHE is a self-reporting instrument that determines the level of disability during specific and usual activities, and also contains some items to determine the level of pain and aesthetics (59). It takes on average 4 minutes to complete the questionnaire (61).

A digital goniometer is used to determine the active ROM. It is expected that the process of measuring ROM takes 6 minutes to complete.

Grip strength is measured using a hydraulic dynamometer (73). The strength of four different grips will be determined, according to the protocol as described by Mathiowetz et al. (1984). It is expected that the procedure to measure the grip strengths takes 4 minutes to measure both sides.

Dexterity is determined using the SODA. The SODA is a performance-based test, which measures the level of disability during activities of daily living (68). We expect that it takes 20 minutes to complete it. Instructions of the SODA will be given according to the protocol described by Van Lankveld et al. (1996).

The level of pain and the level of pain relief are determined using a VAS (75), a self-reporting scale. It is expected that it only will take a few seconds to complete it.

7.4 *Withdrawal of individual subjects*

The patients are free to withdraw from the study at any time, for any reason, and without consequences. Patients are withdrawn when the study coordinator thinks that participation by a

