9. STATISTICAL ANALYSIS

9.1 *Descriptive statistics*

Patient characteristics are presented using descriptive statistics for the potential confounding variables.

Data of the main outcome measure are of interval level of measurement. The ROM and grip strength are of ratio level of measurement. Hence, the descriptive statistics of these outcome measures are presented by the mean and standard deviation. Dexterity is measured using the SODA, and the data of this instrument are of ordinal level of measurement. Therefore, the descriptive statistics are presented by the median and range. Pain is measured using the VAS, which provides data of interval level of measurement. So, the descriptive statistics are presented by the mean and standard deviation.

9.2 *Univariate analysis*

The effectiveness of motor imagery training will be determined with use of a multivariate analysis for the parametric data (as described later in chapter 9.3). The non-parametric data are analyzed using a Mann-Whitney U test for each variable, to determine whether the groups are different. This test is also used when the data is not normally distributed.

9.3 *Multivariate analysis*

With use of a MANOVA, the difference between the experimental and control group will be determined for each measurement time and for each variable. There are two factors included in the analysis; a between factor 'group' and a within factor 'time'. The hypothesis is tested using two-tailed tests, with a significance level of 5%. The data of the patients in both groups will be analyzed using an intention to treat analysis.

9.4 *Interim analysis (if applicable)*

An interim analysis will be conducted to determine the effect of motor imagery training on hand function, dexterity, ROM, grip strength and pain. When the results of this analysis shows serious unwanted effects of motor imagery training, this study will be terminated.

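### ROM and grip strength are measured on both hands to control variability, but the plan does not say how the uninjured-hand values enter the analysis

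*Combined protocol and SAP*

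**What the plan says.** Section 7.1.2 states for ROM: "To control for within-group variability, ROM is measured on both hands". It states the same for strength: "To control for within-group variability, grip strength is measured on both hands". Section 7.3 allows time for it: "It is expected that the procedure to measure the grip strengths takes 4 minutes to measure both sides".

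Section 7.1.3 lists six covariates (age, motor imagery ability, fracture type, occupation, sport, and involvement of the casted hand in activities) and says of them: "The confounding factors will be included in the statistical analysis as covariates to control for their influence". The uninjured-hand value is not among them.

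Section 9.1 summarises ROM and grip strength by mean and standard deviation without naming a hand. Section 9.3 plans a MANOVA for each visit and each variable and adds: "There are two factors included in the analysis". These are group, between patients, and time, within patients. No side factor, ratio, difference or contralateral covariate is defined anywhere.

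**The concern.** Measuring a second hand reduces variability only if its value is used. The plan gives the reason for the measurement but no step that carries it out.

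Two things are at stake.

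- **Precision.** The Summary describes a post-test-only design, so no pre-treatment ROM or grip value exists. The uninjured hand is the only within-patient reference for these outcomes. Without it, natural differences in strength and mobility among women aged 45 to 75 stay in the error term, except for what the six planned covariates explain.
- **Pre-specification.** Section 7.2 says that neither patients nor researcher are blinded, and under 7.3 the study coordinator performs all tests. With six ROM directions, four grips and two visits, there are 6 × 2 + 4 × 2 = 20 group comparisons. For each, the use of the second hand could be settled after the data are seen.

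**Working it through.** **1. The text.** The places where the uninjured-hand value could enter are the covariate list (7.1.3), the descriptive statistics (9.1) and the model (9.3). None mentions it. The statement of purpose in 7.1.2 therefore has no counterpart in the analysis.

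**2. The plan's own figure.** Section 4.4 gives N=52 for PRWHE, from a repeated-measures within-between interaction with f=0.20, two groups, two measurements, alpha 5% and power 80%. Take the unstated default correlation between visits as 0.5 (assumption). Then λ = f²·N·m/(1−ρ) = 0.04 × 52 × 2 / 0.5 = 8.32 on (1, 50) df, and power is 0.807. At N=50 it is 0.791. So 52 is reproduced. It concerns the primary outcome only; the plan gives no power figure for ROM or grip strength.

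**3. Detectable difference without the extra covariate.** Inputs: 26 per arm (52 in equal groups), two-sided 5%, 80% power, comparison at one visit. With λ = d²·26/2 on (1, 50) df, the solution is d = 0.792. The unit is the residual SD before the uninjured-hand value is added. If the six planned covariates take one df each (assumption), error df falls to 44 and the result is 0.795, so their df cost can be ignored here.

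**4. Effect of adding the uninjured-hand value.** Let r be its correlation with the injured-hand value after the planned covariates. Residual variance is multiplied by 1−r², the detectable difference by √(1−r²), and one df is lost. The documents give no value for r, so a range is assumed. The last column is power for a true difference of 0.6 SD, also an assumption.

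| Partial r | Variance factor | Reduction | Detectable difference | Power at 0.6 SD |
|---|---|---|---|---|
| none | 1.00 | – | 0.79 | 56% |
| 0.3 | 0.91 | 9% | 0.76 | 60% |
| 0.5 | 0.75 | 25% | 0.69 | 69% |
| 0.7 | 0.51 | 49% | 0.57 | 84% |
| 0.8 | 0.36 | 64% | 0.48 | 94% |

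**5. Why the partial correlation is the right one.** Suppose the planned covariates together correlate 0.5 with each hand and the raw between-hand correlation is 0.5 (illustration). The partial correlation is (0.5 − 0.5 × 0.5)/(1 − 0.5²) = 0.25/0.75 = 0.33. The further reduction is 0.33² = 11%, not the 25% that the raw value would suggest.

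**6. Why the form matters.** With equal SDs and r now the raw correlation, a simple difference between hands multiplies the variance by 2(1−r): 1.4 at r=0.3, 1.0 at 0.5, 0.6 at 0.7. Below 0.5 it is worse than ignoring the second hand. A covariate costs one df and does no comparable harm when r is low.

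**The case against.** **Silence is not exclusion.** A reader might infer that the plan discards the uninjured-hand data. The documents do not support that. The purpose stated in 7.1.2 is evidence of intended use. Section 9.3 also omits the six covariates that 7.1.3 says will be included, so it is not a full model statement. It does not define the ROM or grip variable either, so a ratio or difference would be compatible with it. This stands: the use is unspecified, not ruled out.

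**The gain may be small.** The plan already adjusts for age, occupation and sport, which may explain part of the same variation, so a comparison with an unadjusted test would overstate the benefit. At T1 the cast has just come off; pain and stiffness may dominate the injured hand and weaken its link with the other. A group-by-time test already removes stable differences between patients, so the gain concerns the comparisons at each visit. All of this stands, and is why the range includes r=0.3.

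**The covariate is measured after allocation.** The mechanism proposed in 1.1 and 1.2 is central, so an effect on the other hand cannot be assumed away. If there is one, adjustment would bias the group contrast. This too stands. The T1 value is preferable to the T2 value, which is taken two weeks later, but T1 itself follows the training period.

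None of this supplies the missing specification.

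**Conclusion.** The point holds as a gap in specification. The plan measures both hands for a stated reason and specifies no analysis that serves it, leaving an avoidable choice to an unblinded team.

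Using the values would be a cheap improvement of uncertain size. It is modest at a partial correlation of 0.3 (0.79 to 0.76 SD) and substantial at 0.7 or above (0.57 SD or less). These figures rest on 26 per arm, a comparison at a single visit and an assumed range of correlations; no particular gain can be promised.

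A reader might also infer that the trial's main result or sample size is compromised. It is not: PRWHE has no second-hand measurement and N=52 is unaffected. Nor does leaving out the uninjured hand in itself make the tests of ROM and grip strength biased or invalid.

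**What to change.** In 9.3, state that the injured-hand value is the outcome for each ROM and grip variable. Add the matching uninjured-hand value at T1 as a covariate at both visits, alongside those in 7.1.3. State the assumption that imagery of the injured wrist does not change the uninjured hand.

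Report uninjured-hand means by arm, and repeat each analysis without this covariate as a sensitivity check. With 26 per arm, similar means are only weak reassurance, so the sensitivity analysis is needed as well.

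The cost is a few sentences in 9.3, one df per model and one extra run of each analysis. No patients, visits or measurements are added. The downside is the reliance on a covariate measured after the training period.

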7.2 Randomization, blinding and treatment allocation

Potential participants are randomly allocated to the experimental or control group before the start of the study, i.e. before inclusion. In this way, the potential participants allocated to the control group can receive other information about this study than potential participants allocated to the experimental group. This is done to prevent occurrence of the bias that might be present when the patients in the control group are aware of the working mechanism of motor imagery, and its potential benefits. When the patients in the control group know that they participate in a study that is conducted to determine whether motor imagery can promote the recovery after DRF, it is possible that they perform motor imagery during the immobilization, or pay more attention to their injured hand as normal. Such bias cannot be detected and may severely confound the results of this study. Therefore, we decided to keep the patients in the control group ignorant.

Because randomization is performed before inclusion, it is likely that some patients will decide not to participate, reducing the number of participants in that group. The experience of 2.5 years inclusion teaches us that the response rate to participate is different for each group (experimental group 35%, control group 62%). Therefore, the number of patients who will be asked to participate is controlled for this difference. This means that more patients are allocated to the experimental group, than to the control group. The random allocation is performed with remaining equal group sizes, and equal distribution of the different fracture types (intra-articular vs. extra-articular distal radius fractures).

The randomization process is done using PASW Statistics 18. Subject numbers are randomly allocated to the experimental or the control group. The order in which the patients receive their initial treatment determines their subject number. There is no blinding of the patients, nor the researcher is blinded.

Based on national statistics concerning the diseases and injuries diagnosed on a yearly basis, it is expected that 6-7 DRF-patients will be treated in the UMCG every week, and 2-3 of them will be women of 45-75 years of age (58).

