7.3 Study procedures

The study coordinator checks the diagnose lists of the department of Traumatology and Orthopedics, and identifies the female DRF-patients in the age of 45-75 years of age, who are conservatively treated. These patients will be randomly allocated to the experimental or control group. They receive an information letter and are asked to participate. When they decide to participate, they return an informed consent. When the patients visit the hospital for a medical check one week after initial treatment, the patients who are willing to participate are asked to fill out the Vividness of Motor Imagery Questionnaire. A score of 72 point or less on the internal scale (first person perspective) of the VMIQ, is one of the inclusion criteria. Therefore, this questionnaire is filled out before inclusion. The score on the VMIQ determines whether the patient can participate in the study or not. The patients who are allocated to the experimental group will receive information and instructions about the motor imagery training. To promote the imagery, the instructions are task-related:

- Flexion and extension: Patients are asked to imagine making a fist and imagine that they are slowly knocking on the table with their knuckles, making an exaggerated large movement.
- Adduction and abduction: Patients are asked to imagine that there are two dots drawn horizontally on the table in front of them. The hand lies between those dots, but there is still space between the hand and the dots. They are asked to imagine that they are trying to touch the right and the left dot with their little finger and thumb repeatedly, by only moving the palm of their hand.
- Pronation and supination: Patients are asked to imagine that they turn a key back and forth, by only using their hand and forearm.

In addition to these task-related instructions, the movements that have to be imagined are demonstrated by the study coordinator. Next, the patients are asked to repeat that movement once with their uninjured hand. The patients receive a letter that contains the instructions and are asked to repeat this protocol unsupervised at home. To promote their adherence to the motor imagery training, the patients in the experimental group will be contacted by phone on a weekly basis. To control for bias as a consequence of this extra attention, also the patients in the control group will be contacted by phone weekly.

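### Section 7.1.3 adjusts for casted-hand involvement, which as worded mostly follows allocation, and section 9 does not carry out the covariate rule

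*Combined protocol and SAP*

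**What the plan says.** Section 7.1.3 lists age, motor imagery ability, "type of fracture, occupation, sport activities and involvement of their casted hand in activities" as possible confounders. It then commits, with no exception by outcome or test: "The confounding factors will be included in the statistical analysis as covariates to control for their influence". No period is given for the hand question. Section 9.1 describes the confounders as patient characteristics.

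On timing, section 7.2 has potential participants "randomly allocated to the experimental or control group before the start of the study, i.e. before inclusion", and neither patients nor researcher are blinded. Section 10.2 sends an arm-specific letter within 48 hours of initial treatment. The VMIQ is completed at the one-week check; section 7.3 notes that "this questionnaire is filled out before inclusion". Training instruction follows. Then: "Three weeks later, which is 4 weeks after injury, the patients return to the hospital to remove the cast".

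On analysis, section 9.2 sends non-parametric data, and any data that are not normally distributed, to a Mann-Whitney U test per variable. Section 9.1 classes the SODA as ordinal. Section 9.3 compares the groups by MANOVA at each measurement time, names group and time as the two factors, and states an intention-to-treat analysis.

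**The concern.** A hand is casted only from initial treatment, so casted-hand involvement as worded is mainly a post-allocation behaviour. Adjusting for a variable that allocation can change removes, or adds, whatever part of the group difference runs through it. The result is then not the total effect that an intention-to-treat comparison aims at.

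The protocol gives some reason to think the arms could differ. Section 7.2 says of control patients who learn the study's purpose that "it is possible that they perform motor imagery during the immobilization, or pay more attention to their injured hand as normal". Controls are kept uninformed for this reason, while the experimental arm is told.

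The exposed quantity is the per-visit group difference in 9.3. It matters here because the Summary describes a post-test only design and section 10.4 expects benefit to be visible when the cast comes off.

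The second problem is one of execution. A rule that covers all analyses cannot be followed by a test that takes no covariates, and 9.3 does not mention covariates. Adjusted and unadjusted results could be mixed across outcomes without the plan saying so.

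**Working it through.** **The plan's own figures.** From section 4.4: target 5.3 points, SD 26.13, so 5.3/26.13 = 0.203, which the plan gives as 0.20. For the repeated-measures interaction with f = 0.20, two groups, two measurements and an assumed default correlation of 0.5, the noncentrality is 0.20² × 52 × 2/(1 − 0.5) = 8.32. Power is 0.8075 at N = 52 and 0.7915 at N = 50, so 52 is reproduced from the entries stated. (Whether 0.20 was entered on the right scale is a separate question.) The powered test is the interaction, and the calculation contains no covariates.

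**Timing.** Assume initial treatment on the day of injury and allocation by day 2.
- 4-week cast: 26/28 = 93% of casted days follow allocation.
- 6-week cast: 40/42 = 95%.
- Counted from training instruction at one week, with a 4-week cast: 21/28 = 75%.

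**Per-visit difference.** Let d be the arm difference in hand use caused by allocation (experimental minus control, in SD), and r the within-arm correlation of hand use with PRWHE. The documents give neither. Leaving aside unmeasured common causes of hand use and outcome:

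adjusted difference = total effect − d × r × SD

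| Size of d and r | Shift with SD 26.13 | Share of 5.3 |
|---|---|---|
| 0 | 0 | 0% |
| 0.1 | 0.1 × 0.1 × 26.13 = 0.26 | 5% |
| 0.2 | 0.2 × 0.2 × 26.13 = 1.05 | 20% |
| 0.3 | 0.3 × 0.3 × 26.13 = 2.35 | 44% |

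At 0.3, a true −5.3 becomes −2.95 or −7.65, depending on sign. Simulation with 26 per arm and 20,000 runs gives −3.00 and −7.61, and −5.31 when d = 0.

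**The SD.** The formula in 4.4 includes a squared difference between occasion means, so 26.13 contains spread between occasions. With equal n, the within-occasion SD is about √(26.13² − (gap/2)²). A 10-point gap gives √(682.8 − 25) = 25.6. An assumed 40-point gap gives √(682.8 − 400) = 16.8, and the largest shift above falls to 0.09 × 16.8 = 1.5 points.

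**Interaction.** The shift is d × (r at T2 − r at T1) × SD. It is zero if r is equal at both visits. With d = 0.2 and a difference of 0.1 in r, it is 0.2 × 0.1 × 26.13 = 0.52 points.

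**The reverse case.** Suppose hand use differs between arms only because different patients agreed to take part (d = 0.2, r = −0.2). The unadjusted difference is then −5.3 − 1.05 = −6.35, and the adjusted one is −5.3.

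**Section 7.1.3 against section 9.** The SODA is certain to go to Mann-Whitney. Any other outcome, PRWHE included, goes there if it is not normally distributed. None of these can be adjusted as planned, and section 9 nowhere says how covariates enter the MANOVA.

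**The case against.** The harm depends on a link that the documents do not make. Section 1.2 has training act on the neural consequences of immobilization and claims no effect on hand use. The 7.2 remark concerns attention, not use, in control patients who know the aim, and they are kept uninformed. Section 7.3 also phones both arms weekly to even out attention. All of this stands: an arm difference is plausible, not shown. The phone calls bear on contact, however, and not on the difference in information between the arms.

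Section 9.1's label, and the placing beside occupation and sport, may mean that a background trait was intended, such as the usual role of that hand. If so, the first half of the point lapses. But the text says casted hand and gives no other period, so the plan needs to settle it.

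The strongest objection is that response differs by arm, "experimental group 35%, control group 62" percent, after allocation and before inclusion. Differential participation is therefore documented, while an effect of allocation on hand use is not. Under the reverse case above, dropping the covariate costs as much as keeping it would in the other case. A reader might infer that the unadjusted estimate is the unbiased one; the documents do not support that. This is why both models should be shown.

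VMIQ score is also taken after the arm-specific letter, so keeping it rests on an assumption that should be stated. Likewise, "equal distribution of the different fracture types" is arranged at allocation, before the unequal response, and need not hold among those included.

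**Conclusion.** The point holds as a matter of specification. As worded, 7.1.3 conditions on a variable that allocation may change, and section 9 does not carry out the covariate rule. The second part follows from the text alone and needs no assumption.

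The size of the first part is unknown. It is zero if allocation does not change hand use. Otherwise it is about 0.3 to 2.4 PRWHE points in either direction for d and r of 0.1 to 0.3 with SD 26.13, and smaller with a within-visit SD.

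A reader might infer that training has been shown to alter hand use, or that the result the trial is powered for stands to lose 44% of its effect. Neither is supported. The 44% needs both assumed values at the top of the range and the larger SD, and it concerns per-visit differences. The powered interaction is untouched with equal correlations and moves by about 0.5 points in the unequal case shown. The change should be made because it is cheap and removes an ambiguity, not because bias has been demonstrated.

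**What to change.** - **7.1.3 and 9.3:** Limit the main model to age, fracture type, VMIQ score, and occupation and sport asked as pre-injury status, and name these covariates in 9.3. Note that the VMIQ follows the arm-specific letter but precedes training instruction, and is assumed unaffected by the letter. Note also that fracture type was balanced at allocation, before differential consent.
- **Casted-hand involvement:** Ask it with the same wording in both arms and report it by arm. Give a model that includes it as a prespecified sensitivity analysis beside the main one. If pre-injury use of that hand is meant, ask it that way and keep it as a covariate.
- **9.2:** State that Mann-Whitney comparisons are unadjusted. Add a rank-based or ordinal analysis that takes the same covariates as a sensitivity analysis.

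The cost is wording, plus a time frame for three questions. For precision, going from six covariates to five (one term each) with 52 patients gives a variance ratio of (43/44)/(1 − r²). This is 1.00 at r = 0.15 and 1.074 at r = 0.3, where the standard error is about 4% larger. The main downside is that, if the unequal response leaves the arms different in activity, the main model gives up some adjustment for it, worth the same assumed 0.3 to 2.4 points. Pre-injury occupation and sport recover part of this, and the sensitivity model shows how far the estimate moves when hand use is added.
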